Randomization Patients who pass the screening will be randomized into one of the four groups using a centrally generated, variable-sized block design.

Endpoints

Primary outcomes

The primary outcome will be blood oxygen level (BOLD) response (fMRI signal) differences evoked by V-GAIT and V-GAIT control.

Secondary outcomes

Secondary outcomes will include 1) PAG resting state functional connectivity differences before and after one month of treatment; 2) KOOS Score [30] (we will focus on KOOS pain subscale score based on previous studies [2, 31-33]) and other clinical outcomes (see below for details); and 3) QST [1, 34]. All clinical outcomes will be measured at baseline and after the last treatment.

PAG-ACC/mPFC resting state functional connectivity will be assessed by calculating Pearson's correlation between the fMRI scan time courses of the PAG and ACC / MPFC using the CONN toolbox [35], while the subject is resting in the fMRI scanner prior to beginning the treatment and again immediately after the treatment. In short, preprocessing of resting state fMRI data will

include co-registration, motion correction, normalization to MNI stereotactic space, and spatial smoothing with an 8 mm Gaussian kernel. Functional connectivity analysis for individual subjects will be carried out using the PAG as a seed. Specifically, the average time course of the PAG will be obtained and correlation analysis will be performed in a voxel-wise way to generate a functional connectivity map for PAG. The resulting correlation coefficient map will be converted into a Fisher-Z map using Fisher's r-to-z transformation to improve the normality, and then will be entered into the group analysis. Group analysis will be performed using CONN toolbox [35]. A full factorial module in SPM 12 will be performed to compare the PAG rsFC changes before and after about one month of VGAIT, VGAIT control, real and sham treatments.

Blindness During data acquisition, all study personnel except the administering acupuncturist will be blinded with respect to treatment conditions. Patients will also be blind to acupuncture modality (real or sham) they receive till end of the study, a study investigator will debrief the subject and explain the rational of blindness.

Experimental procedure

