Clinical and psychometric measurements All clinical assessments will be completed by patients during their first visit (session 1) and during their last visit (session 8). Question 6 (pain rating now, 0-10 scale) of the BPI and ERS will be repeated at the beginning and end of all fMRI scan sessions. The MASS will be administered after all treatments. The complete KOOS and BPI will be administered during patients' first and final study visits.

Knee Injury and Osteoarthritis Outcomes Score (KOOS): The KOOS is a 35-item self-administered survey of pain and function in knee OA patients [30]. It contains the WOMAC

items (Western Ontario and McMaster Universities Osteoarthritis Index) and additional items for pain and functional ratings. It may be more sensitive to subtle improvements in function than the WOMAC [39]. KOOS is comprised of 5 subscales: 1) pain, 2) other symptoms, 3) function in daily living (ADL), 4) function in sport and recreation, and 5) knee-related quality of life (QOL). Each subscale allows for calculation of a normalized score, with 0 denoting the most extreme symptoms/pain and 100 denoting no symptoms/pain [30]. Based on previous studies [2, 31-33], we will focus on the KOOS pain subscale.

Brief Pain Inventory (BPI): The BPI is a 15-item questionnaire rating pain location, intensity, relief, and quality, as well as pain-related quality of life, and it has been validated in many pain studies [40, 41].

Beck Depression Inventory (BDI): The 21-item BDI has shown good sensitivity and specificity for major depression in chronic pain patients [42, 43]. BDI scores greater than 20 will be considered high for depression symptoms [42].

MGH Acupuncture Sensation Scale (MASS): The MASS includes 12 descriptors of common acupuncture sensations: soreness, aching, deep pressure, heaviness, fullness/distension, tingling, numbness, sharp pain, dull pain, warmth, cold, and throbbing with one supplementary row at the end of the descriptors for subjects to describe their perceptions in their own words [25]. We have developed an EPrime script that allows us to collect subject MASS ratings while they are in the scanner, using a projector and a button response system.

Betts' Questionnaire upon Mental Imagery (BQMI): We will use the BQMI to measure the imagery vividness of VGAIT in this study. The BQMI consists of 35 items. Each item of image vividness is rated on a 7-point scale, and the procedure is undertaken with the eyes open.

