Expectations for Relief Scale (ERS): The ERS is a 0-10 scale used to measure the expectation of post-acupuncture pain relief. During every fMRI scan session, after each verum or placebo acupuncture treatment, subjects will be asked to use the scale to rate how much pain relief they expect from this particular treatment, with 0 indicating a very negative expectation of "does not work at all" and 10 indicating a very positive expectation of "complete pain relief." Studies have shown that expectation can significantly influence an individual's perception of pain relief [44-50].

State-Trait Anxiety Inventory (STAI): The STAI consists of two 20-item self-report inventories. It is a rapid but detailed assessment that distinguishes between basal (part one inventory) and reactive (part two inventory) anxiety [51]. Scores range from 20 to 80 with higher scores indicating a greater level of anxiety. Some studies suggest that subjects with high initial anxiety scores tend to experience more pain relief after acupuncture treatment than those with low anxiety scores [52, 53].

Sessions 2-7 are acupuncture treatment visits. Session 2 (treatment 1) will be applied in the fMRI scanner. Based on previous studies from other groups [2, 54, 55] and our group [31, 32, 56, 57], we decided to administer treatment six times in about one month (approximately two times per week for the first two weeks and one time per week for the last two weeks). While we prefer study sessions to occur at these intervals, scheduling adjustments can be made without affecting the integrity of the research. The rationale for this is that the effects of acupuncture have been shown to last up to six months following the intervention, so slight adjustments to the preferred treatment plan are not consequential to treatment effects.

All brain imaging will be performed with a 3-axis gradient head coil in a 3 Tesla Siemens MRI System equipped for echo planar imaging. A high-resolution 3D MPRAGE sequence will be collected for anatomic localization of significant signal changes. Functional MRI images will be acquired using a gradient echo T2*- weighted pulse sequence (TR/TE = 2000/30ms, flip angle =

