90°, FOV = 192x192 mm, 48 AC-PC aligned slices, slice thickness = 3.0 mm with 0.6 mm inter-slice gap, 90 image volumes per slice, matrix = 96x96). fMRI scans will include one resting state scan (8 minutes) during which subjects will be told to open their eyes and two ten-minute scans of different treatments, which is identical to our previous study.

All participants will be asked to fill out the MGH Acupuncture Sensation Scale (MASS) following each treatment. Additionally, participants randomized to the video conditions will fill out the Vividness Scale. The Vividness scale will use a 0-10 vividness scale to measure imagery vividness during the fMRI scans. The scale ranges from Not Vivid/Unclear (0) to Vivid/Clear (10).

Session 8 will involve a resting state MRI scan. In addition, subjects will complete the clinical and psychometric measurements used during session 1 and undergo QST testing. Subjects will complete the Final Questionnaire during this session and EEG data will be collected.

Procedures for video guided acupuncture imagery treatment and control condition

VGAIT and control conditions will last about 25 minutes; the time is the same as real acupuncture (see the following for details). The same licensed acupuncturist will carry out the VGAIT and control conditions.

Procedures for acupuncture administration Similar to our previous studies [31, 32, 56, 57], acupuncture procedures will last approximately 30 minutes in total and will be carried out by a licensed acupuncturist on the side with the most severe symptoms or the side as chosen by subjects to need more treatment.

Verum acupuncture procedures Verum acupuncture will be applied on ST35, Xi Yuan (extra point), GB34, SP9, GB39, and SP6 based on literature [2, 32, 54, 56-60]. After insertion and obtainment of *deqi* sensation, needles will be manipulated in the order of GB34, SP9, ST35, Xi yuan (extra point), GB39, and SP6.

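### Month-end pain is collected only at session 8, and nothing asks patients who stop treatment to provide it

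*Protocol*

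**What the plan says.** Protocol section V gives the timing of the clinical outcomes in several places, and they agree.

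- Secondary outcomes: "All clinical outcomes will be measured at baseline and after the last treatment".
- Clinical and psychometric measurements: "All clinical assessments will be completed by patients during their first visit (session 1) and during their last visit (session 8"), and "The complete KOOS and BPI will be administered during patients' first and final study visits".
- Session 8 description: "subjects will complete the clinical and psychometric measurements used during session 1 and undergo QST testing".

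Between those two points, the only knee-pain rating is question 6 of the BPI, a 0-10 rating of pain now. It and the ERS "will be repeated at the beginning and end of all fMRI scan sessions". Two scan sessions are described. For the first, "Session 2 (treatment 1) will be applied in the fMRI scanner". The other is session 8, with a resting-state scan. On the treatment course the protocol says "we decided to administer treatment six times in about one month", which fills sessions 2 to 7.

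The MASS is completed after every treatment, but it rates acupuncture sensations. The vividness scale applies only to the video arms and is described for imagery during the scans.

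KOOS, with the pain subscale as its focus, is a secondary outcome. The SAP covers the primary fMRI outcome only. Neither document has an early-termination assessment, a rule for following patients who stop treatment, a KOOS analysis set or a KOOS missing-data method.

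**The concern.** A pain outcome measured once after baseline, at the end of a one-month course, exists only for patients who reach that visit. Five of the six treatments fall in sessions 3 to 7, where no knee-pain rating is described. A patient who leaves in that window has a baseline KOOS and single-item ratings around the first treatment, but nothing at month end.

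People who leave are unlikely to be a random subset, and repeated needling and watching a video are different experiences, so neither the rate of leaving nor the reasons can be presumed equal across arms. If those who leave tend to be doing worse, a change score computed in the remainder looks too favourable, and more so in the arm that loses more.

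Hypothesis 1.2 (Protocol section II) needs month-end pain twice: for the reduction after VGAIT and real acupuncture, and for the association of that reduction with the treatment-evoked fMRI signal. Hypothesis 2.2 needs it for the association with the change in connectivity.

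**Working it through.** The documents give no dropout rate, standard deviation or power figure for KOOS, so there is no planned figure to reproduce. The check has three parts.

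**1. What is scheduled when (Protocol section V)**

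| Session | Complete KOOS and BPI | BPI question 6 |
|---|---|---|
| 1 (baseline) | yes | within the BPI |
| 2 (treatment 1, scanner) | no | start and end |
| 3 to 7 (treatments 2 to 6) | no | none described |
| 8 (after last treatment, scanner) | yes | start and end, and within the BPI |

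A patient who leaves during sessions 3 to 7 and does not attend session 8 has no post-baseline KOOS and, on the sessions described, no pain-now score after session 2. A change from baseline cannot be computed for that patient, and no alternative is stated.

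**2. Bias if only patients with session 8 data are used**

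Let d be the proportion of an arm without session 8 data and g the mean change in those with data minus the mean change in those without (KOOS points, higher is better).

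- Mean change in the whole arm = (mean in those with data) − d × g, so within-arm improvement is overstated by d × g.
- The between-arm difference is biased by d1 × g1 − d0 × g0, which is (d1 − d0) × g when the gap is the same in both arms.

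All values of d and g below are assumptions.

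| Within arm | g = 5 | g = 10 | g = 20 |
|---|---|---|---|
| d = 10% | 0.5 | 1.0 | 2.0 |
| d = 20% | 1.0 | 2.0 | 4.0 |
| d = 30% | 1.5 | 3.0 | 6.0 |

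| Between arms, common gap | g = 10 | g = 20 |
|---|---|---|
| d1 − d0 = 0 | 0 | 0 |
| d1 − d0 = 10 points | 0.10 × 10 = 1 | 0.10 × 20 = 2 |
| d1 − d0 = 20 points | 0.20 × 10 = 2 | 0.20 × 20 = 4 |

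The within-arm table bears on the first part of Hypothesis 1.2, which is a reduction after treatment. The between-arm table bears on any KOOS comparison of groups.

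**3. Loss of precision**

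With equal allocation (the ratio is not stated), 125 / 4 = 31.25 per arm. The standardised difference detectable with 80% power at two-sided 0.05, for one pairwise comparison, is (1.96 + 0.84) × √(2/n), or 0.71 at full size. Losing 5%, 10%, 20% or 30% leaves 29.7, 28.1, 25.0 or 21.9 per arm and raises it to 0.73, 0.75, 0.79 or 0.85. At modest dropout, precision suffers little. Selective loss is the larger worry.

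**The case against.** Several points on the other side have force.

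- **Stopping treatment is not missing session 8.** Nothing bars a patient who stops from attending, and timing the outcome after the last treatment does not require all six treatments. This stands: the text is silent and specifies no exclusion. But silence also means nobody is asked to return. If the final visit means whichever visit is last, a patient who leaves unannounced is still missed and the others are measured at differing times.
- **A reader might infer a completers-only analysis.** No KOOS analysis set is stated, so that is only the default outcome of the schedule, not a planned rule.
- **A reader might infer that the trial cannot see worsening.** KOOS runs from 0 to 100 and records deterioration in everyone assessed at session 8, and the MASS captures painful needling sensations at each treatment. What can be lost is knee-pain worsening in those who leave first. Nor do the documents support a claim that a safety signal is hidden: KOOS is an outcome score, and the protocol refers to attachments not included here.
- **A reader might take 125 − (24 + 25 + 23 + 26) = 27 as a loss rate.** It is a recruitment target minus an fMRI analysis count. The only stated exclusion reason is head movement, and the described treatment scan precedes sessions 3 to 7. It says nothing about KOOS.
- **Other scanned sessions may exist.** The ERS wording about every scan session would allow further scanned treatments, each with a pain-now rating, but none is described. The week 8 and follow-up contacts under Blood marker test are mentioned only for blood samples and do not fit the eight-session schedule; those passages need reconciling.
- **KOOS is secondary.** True, and it limits the weight of the point.

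**Conclusion.** The point holds in a limited form. Followed as written, the plan has one post-baseline KOOS and BPI assessment and no provision to obtain it from patients who stop treatment. Those who leave during sessions 3 to 7 would by default have no month-end pain score. That can bias KOOS pain and the pain parts of Hypotheses 1.2 and 2.2. The primary outcome does not depend on session 8, because the treatment-evoked response is described as scanned at session 2.

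The size is unknown. The 1 to 4 KOOS points between arms rest entirely on assumed dropout differences and an assumed outcome gap, and with equal dropout and an equal gap the between-arm bias is zero, although each arm's own improvement would still be overstated. This is a worthwhile, inexpensive improvement, not a defect that undermines the trial's main result.

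**What to change.** **Data collection (Protocol section V, Clinical and psychometric measurements).** State that KOOS and BPI are collected from every randomised patient at the planned session 8 time, whether or not treatment was completed. Patients who do not attend complete them through REDCap, which section III already names for eConsent. Telephone is a last resort, with the mode recorded. Record the reason for stopping at the same contact. Add BPI question 6 at the start of sessions 3 to 7 as supporting data, not as a substitute for KOOS.

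**Analysis and reporting (SAP).** Analyse KOOS pain by randomised group with a stated missing-data method and a sensitivity analysis for non-ignorable loss. Report by arm the numbers randomised, stopping early and providing session 8 KOOS.

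The SAP describes imaging in the past tense. If collection has finished, only the analysis and reporting part applies.

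**Cost.** One remote contact per patient who stops, one 0-10 item at five existing visits, and a possible mode difference for KOOS completed remotely. Remote completion supplies no second resting scan, so it helps Hypothesis 1.2 more than Hypothesis 2.2.

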As an invasive treatment, acupuncture involves needle insertion and manipulation. Literature suggests that *deqi* (sensations evoked by acupuncture needle manipulation such as soreness, aching, and dull pain) are crucial for treatment effects [24-26]. To the extent that these acupuncture sensations can be elicited by watching a video of acupuncture treatment and imagining the treatment, one would expect that brain activity changes would be produced that overlap with those changes produced by real acupuncture needle manipulation. Indeed, this has been demonstrated by a previous brain imaging study in which investigators found that visualizing images of acupuncture needle stimulation [27] produced overlapping fMRI signal changes in the brain at the anterior insula (AI), middle cingulate cortex (MCC)/dorsal anterior cingulate cortex (dACC), and periaqueductal grey (PAG).

Taken together, these findings provide a solid foundation for VGAIT. Most importantly, applying powerful brain imaging tools to explore the neuroscience of mind-body interaction and then testing its treatment effect in a patient population may elucidate how the mind can alter perception [11] and thereby reshape pain experience to achieve a therapeutic effect.

II. SPECIFIC AIMS

The aim of this proposal is to investigate brain response and connectivity changes evoked by video-guided acupuncture imagery treatment (VGAIT) and verum and sham acupuncture in patient populations to elucidate the underlying brain mechanisms of mind-body interaction, imagery, and acupuncture.

Specific Aim 1: Characterize and compare the brain response evoked by VGAIT, a VGAIT control condition, and real and sham acupuncture in chronic pain patients.

Hypothesis 1.1 VGAIT and real acupuncture will produce overlapping fMRI signal increases in AI, MCC/dACC, and PAG as compared to control and sham acupuncture. Real acupuncture will produce greater fMRI signal increases at primary somatosensory cortex (S1) compared to VGAIT in OA patients.

Hypothesis 1.2: Pain intensity ratings of the OA patients will be reduced after about one month of VGAIT and real acupuncture treatment; fMRI signal increases at AI, MCC/dACC, and PAG evoked by treatment will be associated with knee pain intensity reduction after about one month treatment.

Specific Aim 2: Characterize and compare the modulation effects of different treatments on resting state functional connectivity (rsFC) in chronic pain patients.

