Hypothesis 2.1: After treatment, the PAG rsFC with ACC/MPFC will be significantly enhanced in the VGAIT and real acupuncture groups, compared to the control condition and sham acupuncture groups.

Hypothesis 2.2: The PAG-ACC/MPFC rsFC increase will be significantly associated with corresponding knee pain intensity reduction.

III. SUBJECT SELECTION

Inclusion/exclusion criteria for patients with knee OA:

125 male and female patients aged 40-75 with a diagnosis of knee osteoarthritis and pain will be recruited for the experiment. A written informed consent form or REDCap eConsent will be obtained in all cases.

Inclusion Criteria:

- a) Volunteers 40-75 years of age
- b) Meet the Classification Criteria of the American College of Rheumatology for osteoarthritis of the right and/or left knee for at least the past 3 months, as determined by the referring physician
- c) Ability to read and understand English; English can be a second language provided that the patient feels he or she can understand all the questions used in the assessment measures.

Exclusion Criteria:

- a) Any interventional procedure for knee pain, including corticosteroid injections (within 2 months [28, 29]) to the knee
- b) Prior acupuncture treatment for any condition within the past year
- c) The intent to undergo surgery during the time of involvement in the study
- d) Presence of any illness, medication use, or condition that is judged by the principal investigator to interfere with the trial. For example: skin irritations around the knee such as psoriasis, bleeding disorders or anticoagulant use that would be contraindications for acupuncture, diabetes due to the increased possibility of sensitivity to heat pain, or substance abuse. Use of opiates or other medications is allowable if the participant has been taking a stable dosage of the medication for at least one month. Per the judgment of the principal investigator, we may perform a urine toxicology screen to verify a patient's medication status during Session 1. A positive drug test is not exclusionary unless it contradicts the patient's self-report or indicates the presence of illegal substances.
- e) Knee pain due to other causes such as inflammation or malignancy, other pain disorders that may refer pain to the leg, OA of ipsilateral hip, diagnosis of RA
- f) Non-ambulatory status. Assistive devices such as walkers/canes are allowable given that patients do not require assistance with said device.

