**Title: Mechanistic Studies on Video-guided Acupuncture Imagery Treatment of Knee Pain**

**Clinical trial ID: NCT03261505**

**Date: 11/8/2023**

## Statistical plan for primary outcome

**Primary outcome:** fMRI signal changes evoked by the different interventions.

**fMRI data acquisition** All brain imaging was performed with a 3-axis gradient head coil in a 3 Tesla Siemens MRI System equipped for echo planar imaging. A high-resolution 3D MPRAGE sequence was collected for anatomic localization of significant signal changes. Functional MRI images were acquired using a gradient echo T2\*-weighted pulse sequence (TR/TE = 2000/30ms, flip angle = 90°, FOV = 192x192 mm, 48 AC-PC aligned slices, slice thickness = 3.0 mm with 0.6 mm inter-slice gap, 90 image volumes per slice, matrix = 96x96).

**Data analysis:** SPM 12 was applied to investigate the brain responses to different interactions. Preprocessing included co-registration, motion correction, normalization to MNI stereotactic space, and spatial smoothing with an 8 mm Gaussian kernel. For each subject, the contrast between manipulation and no manipulation during acupuncture and sham acupuncture was calculated using a general linear model. The same procedure was followed for V-GAIT and control touching. For V-GAIT, the contrast was between watching/imagining needle manipulation vs. no manipulation, and for the control, contrast was between cotton swab touching vs. no manipulation.

Group analysis was performed using a random-effects model. A one-sample t-test was performed to compare the fMRI signal changes during manipulation vs. no manipulation within each treatment. Then, ANOVA was used to compare the differences among treatment groups. Thresholds of  $p < 0.005$  and  $p < 0.05$  small volume corrected were applied for the region of interest (ROI). Thresholds of  $p < 0.005$  uncorrected and  $p < 0.05$  Family-wise Error (FWE) corrected were used for non-ROI. Based on previous studies and our hypothesis, the ROIs included: the cingulate cortex, insula, primary and secondary somatosensory cortex, dorsal lateral prefrontal cortex, medial prefrontal cortex, inferior parietal lobule, and periaqueductal grey (PAG).

Some subjects were excluded from the MRI data analysis due to the poor quality of the MRI signal due to head movement during the MRI scan. The number of subjects used in this analysis was: 24 for real acupuncture, 25 for sham acupuncture, 23 V-GAIT, 26 V-GAIT control.

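### The treated knee differs between patients and the SAP states no handling of side, so the real acupuncture versus V-GAIT comparison at S1 can lose power

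*Protocol*

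**What the plan says.** - **Eligible knee** (Protocol III, inclusion criterion b): patients may have "osteoarthritis of the right and/or left knee for at least the past 3 months", so eligibility does not fix a side.
- **Treated side** (Protocol V, Procedures for acupuncture administration): treatment is given "on the side with the most severe symptoms or the side as chosen by subjects to need more treatment".
- **Hypothesis** (Protocol II, Hypothesis 1.1): "Real acupuncture will produce greater fMRI signal increases at primary somatosensory cortex (S1) compared to VGAIT in OA patients". No hemisphere is named.
- **Preprocessing** (SAP, Data analysis): "Preprocessing included co-registration, motion correction, normalization to MNI stereotactic space, and spatial smoothing with an 8 mm Gaussian kernel". A left-right flip is not in the list.
- **Group model** (SAP, Data analysis): one-sample t-tests within each treatment, and "Then, ANOVA was used to compare the differences among treatment groups". No side factor or covariate appears.
- **Regions** (SAP, Data analysis): the ROI list begins "the cingulate cortex, insula, primary and secondary somatosensory cortex, dorsal lateral prefrontal cortex". S1 and S2 are included without a hemisphere.
- **Primary outcome** (Protocol V, Endpoints): "The primary outcome will be blood oxygen level (BOLD) response (fMRI signal) differences evoked by V-GAIT and V-GAIT control". The SAP defines it more widely, as signal changes across the different interventions.

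The protocol's randomization paragraph mentions variable-sized blocks only, so side is not stated to be balanced between arms.

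**The concern.** Input from one leg reaches mainly the opposite S1. This is general anatomical knowledge; the documents do not state it. Once images are in a common space, a given S1 voxel is contralateral to the needle in some patients and ipsilateral in others. Averaging over them shrinks the mean response in the real acupuncture arm and adds between-patient variance.

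S1 is the one region where Hypothesis 1.1 predicts that real acupuncture and V-GAIT differ. A null result there could be read as imagery matching needling when it partly reflects mixed sides.

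**Working it through.** The documents give no power, effect size or SD for this comparison, so there is no planned figure to reproduce. What follows is an illustration over stated ranges.

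**Inputs from the documents.** The SAP's analysed numbers are 24 for real acupuncture and 23 for V-GAIT, so df = 24 + 23 − 2 = 45. The ROI thresholds are p<0.005 and p<0.05 small volume corrected; sidedness is not stated.

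**Assumptions.**
- d = 0.8 SD is the real minus V-GAIT difference in contralateral S1.
- p is the share of patients for whom the voxel is contralateral: 0.9, 0.7 or 0.5.
- q is the ipsilateral response as a share of the contralateral one: 0, 0.5 or 0.75.
- V-GAIT has mean 0 and SD 1.

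**Formulas, one fixed voxel.**
- Real-arm mean = d[p + (1−p)q]
- Real-arm variance = 1 + [d(1−q)]² p(1−p)
- Pooled variance s² = (23 × real-arm variance + 22 × 1)/45
- Noncentrality = mean / √[s²(1/24 + 1/23)], with power from the noncentral t on 45 df

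**Aligned.** The standard error is √(1/24 + 1/23) = 0.292 and the noncentrality is 0.8/0.292 = 2.74. Power is 77% at two-sided 0.05.

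**Pooled 50/50, q = 0.** The mean is 0.8 × 0.5 = 0.40 and the variance is 1 + 0.64 × 0.25 = 1.16. Then s² = (23 × 1.16 + 22)/45 = 1.082, the standard error is 0.303 and the noncentrality is 1.32. Power is 25%.

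**Power at one voxel, d = 0.8**

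| Threshold (two-sided) | Aligned | q | 90/10 | 70/30 | 50/50 |
|---|---|---|---|---|---|
| 0.05 | 77% | 0 | 66% | 44% | 25% |
| 0.05 | 77% | 0.5 | 72% | 62% | 51% |
| 0.05 | 77% | 0.75 | 74% | 70% | 65% |
| 0.005 | 43% | 0 | 32% | 15% | 6% |
| 0.005 | 43% | 0.5 | 37% | 28% | 20% |
| 0.005 | 43% | 0.75 | 40% | 35% | 30% |

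At one-sided 0.005, which fits the directional hypothesis, power is 53% aligned and 10% to 50% pooled over the same range. With q = 1 there is no loss.

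**Bilateral S1 volume.** The SAP names no hemisphere, so a search over both is a natural reading. This was simulated with 40,000 trials per setting, one voxel per hemisphere, independent noise, and Bonferroni for two at an overall two-sided 0.05.

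| q | Aligned | Pooled 90/10 | Pooled 70/30 | Pooled 50/50 |
|---|---|---|---|---|
| 0 | 67% | 56% | 38% | 31% |
| 0.5 | 73% | 70% | 65% | 64% |
| 0.75 | 80% | 79% | 79% | 79% |

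**False positives.** With the same lateralised response in both arms, random side and two-sided 0.05, simulated type I error was 4.9% to 5.1% (60,000 trials per setting). A repeat run gave 4.7% to 5.1%. The problem is lost sensitivity.

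**The case against.** The strongest reply is that this rests on silence in a very short SAP. It is a past-tense summary, and it names no motion regressors, covariates or ROI masks either. A flip or a contralateral mask could have been used and not reported. The protocol also points to earlier studies by the same group, where side handling might be described. That stands as a possibility, but nothing in the documents confirms it. It is the reason to ask how side was handled before assuming that it was ignored.

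The size is also open to challenge. The side split, the ipsilateral share and the 0.8 SD are all assumed. The steepest losses belong to a single voxel with no ipsilateral response. With a bilateral volume and a substantial ipsilateral response, the loss is small. The aligned figures are a best case, because the model charges nothing for natural hemispheric asymmetry and gives V-GAIT no S1 response. All of this stands, and it is why the result is given as a range.

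Two limits on scope also stand. The side in the V-GAIT arm is inferred: the video shows the patient's own session 1 acupuncture, so the filmed side presumably varies too. And the protocol's primary contrast, V-GAIT against its control, is little affected, as are the midline regions (MCC/dACC and PAG).

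None of this removes the point that the steps as written give a less sensitive S1 test than an aligned analysis would, unless nearly all patients were treated on one side or the S1 response is close to bilateral. The documents support neither exception.

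**Conclusion.** The concern holds as a modest, inexpensive improvement. The treated side can vary and no handling of it is stated. Pooling sides can therefore reduce power for real acupuncture over V-GAIT at S1.

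Under the assumptions above, the loss ranges from trivial (80% to 79%, bilateral volume, large ipsilateral response) to severe (77% to 25%, one voxel, even split, no ipsilateral response). Where the trial falls in that range cannot be read from the documents. Confidence is medium. The consequence is confined to S1, and possibly S2, in the comparison with V-GAIT. A null S1 finding should not be taken as evidence of no difference until side has been dealt with.

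**What to change.** 1. State whether side was handled and, if so, how. If maps were flipped or a contralateral mask was used, one sentence closes the point.
2. If not, test the S1 comparison on the contrast estimate from S1 contralateral to the treated knee (the filmed knee in the video arms), or flip maps to a common treated side.
3. Add treated side as a factor in the four-group model and tabulate side by arm. The table would also show any chance imbalance, which could itself look like a left-right S1 difference.
4. Keep the unflipped model as a sensitivity analysis. Treat S2 the same way, only as a secondary check.
5. Because the SAP is written in the past tense, label the aligned analysis as added later if results were already known.

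**Cost.** A little extra analysis and no new data. Side must be recoverable: no passage says it was recorded, so the video arms would rely on the session 1 recordings and the needle arms on treatment records. Flipping and a contralateral region both mix left and right hemispheres across patients. Natural asymmetry therefore remains, and the side factor absorbs it only in part.
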